3. Discovery of Novel Molecular Targets. Our secondary outcomes will include exploration of the role of novel regulatory proteins in relation to the changes in amino acid transport associated with T2DM. The basic assumption is that chronic and acute sarcopenia accelerators may reduce amino acid transport with different mechanisms. Thus, we will determine the potential role of newly identified amino acid sensing pathways such as the Sestrins-GATOR1/2 and the lysosomal vATPase/SLC38A9/Regulator complex in the activation, or lack of thereof, of mTORC1 signaling and amino acid transporter expression and function.

Our approach — unique and substantially different from the status quo — is expected to unravel the key underlying mechanisms responsible for accelerated sarcopenia due to T2DM. The knowledge generated by our studies is needed to develop future evidence-based clinical trials of interventions.

3. Concise Summary of Project:

Subjects. We will test our central hypothesis in community dwelling, independent older adults with non-insulin dependent T2DM. Since data previously gathered on healthy subjects will serve as controls for T2DM subjects, who are expected to be overweight or obese, we will limit inclusion to subjects with BMI 23-35 kg/m². Those who have a BMI ≥ 35 kg/m² will be considered for inclusion on a case-to-case basis, depending on whether or not thigh adiposity would impair muscle biopsy. Morbidly obese, frail or exercise trained subjects will be excluded, as these conditions can significantly impact muscle protein metabolism^{13,79,89}, confounding the results. Subjects will be weight stable, as active weight loss in obese older adults can temporarily improve the response of muscle protein synthesis to anabolic stimuli⁸⁸. The study will enroll 80 subjects who will be recruited from the UTMB Pepper Center Volunteer Registry, the Diabetes Clinic for Seniors directed by [name], the UTMB Stark

Diabetes Center ([name]), referral from other UTMB physicians, and advertisement in local media. To aid in subject retention and encourage study adherence, transportation to and from study visits via Lyft will be offered to subjects at no cost to them. We will use the UT System Lyft contract and desktop app, so that subjects will not need to own or use a private smartphone to benefit from this service.

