protein turnover as well as the amino acid transport rates through LAT1 (Phe, Leu), SNAT2 (Gly), and PAT1 (Gly)^{55,93}. To reach the intracellular space, amino acids have to first be transported across the endothelium and then across the muscle fiber membrane⁶⁶. To reduce risks we will use arterialized blood samples, rather than arterial blood, to measure arterial amino acid concentrations and enrichments. This method has been previously validated for amino acid and other metabolite concentrations⁸, and we have preliminary data indicating that it is also valid for amino acid enrichments. Whenever possible we will also perform a Flow Mediated Dilation test to detect endothelial function using Doppler Ultrasound and Near Infrared Spectroscopy. After an approximately 4-hr baseline period, subjects will ingest the assigned amino acid mixture, as a bolus. The mixture will contain EAA in the pattern found in animal protein²² and will be enriched with L-[ring-¹³C₆]-phenylalanine, L-[5,5,5-²H₃]-leucine to maintain the isotopic steady state²² (labeled glycine will not be added because it is not included in the oral mixture). Large vessel blood flow will be measured by Doppler^{86,87}. Microvascular nutritive flow is emerging as a potential regulator of muscle amino acid and protein metabolism⁸⁵⁻⁸⁷. Thus, we will measure it in the basal state (see above) and after amino acid ingestion using Near Infrared Spectroscopy (NIRS) and measuring blood flow using Doppler Ultrasound. Frequent blood samples will be collected during the last hour of the basal period and the first and third hour of the amino acid period to measure amino acid concentrations and enrichments, glucose, insulin, cytokines and endothelin-1. T2DM is characterized by hyperglycemia, hyperinsulinemia, inflammation and endothelial dysfunction, which may have an impact on muscle protein metabolism^{69,86}. Additional serum samples will also be collected and stored for future analyses (e.g. other hormonal assays, proteomics, metabolomics). Two muscle biopsies will be taken in each period to measure all pertinent amino acid and protein kinetic parameters, cross-sectional area, cell signaling, novel regulatory pathways, and gene expression (see Analytical Methods). A portion of the biopsies will be collected for immunohistochemistry. A third incision may be made should the need arise. At the end of the experiment catheters will be removed and subjects will be given a meal. The metabolic study will take approximately 8 hours.

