All unanticipated, serious, fatal and/or life-threatening adverse events will be reported to the IRB within 24h of occurrence. The IRB and the PI will be responsible for determining whether modifications to the protocol and consent form are required. If a determination is made that participants are found to be exposed to excessive risks in relation to anticipated benefits, the study will be immediately suspended. Studies will not resume until modifications are made that are deemed to result in an acceptable risk/benefit ratio by the PI and the IRB. Aggregate reports of adverse events will be prepared as mandated and forwarded to the IRB and ITS-CRC for review.

Plan for Adverse Event Reporting. The PI will be responsible for evaluating each adverse event and determining attribution as well as the impact on the risk/benefit ratio, using the following Grading and Attribution criteria:

Mild – transient laboratory test alterations that do not suggest injury; discomfort noted but no disruption of daily activities; no therapy, or only symptomatic therapy required.

Moderate – Laboratory test alterations indicating injury without long-term risk, discomfort sufficient to modify normal daily activity, specific therapy required (i.e., more than symptomatic).

Serious – laboratory tests indicating a serious health threat or permanent injury, incapacity, inability to work, or to perform normal daily activity, hospitalization required or prolonged, emergency treatment required, life-threatening events, death.

The attribution scale assesses the relation of the event to the study procedures. [name] will judge whether an adverse event is: 1) *not related*; 2) *possibly related*; 3) *probably related*; or 4) *definitely related to the study interventions*.

Table 1. Groups for Aim 1. Older adults with T2DM and healthy controls will be randomized to two groups (n=8/group) receiving 7 g or 21 g of EAA.

	Essential Amino Acid Dose	
	7 g	21 g
Control	C7	C21
T2DM	D7	D21

12. Procedures to Maintain Confidentiality:

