All study data will be collected in REDCap by the research team. Paper data flow sheets or case report forms will be stored in locked file cabinets in a secure area of the PI's recruitment office. Interim data will be reviewed by the PI. Any appearance of a Conflict of Interest by the research team will be avoided by the periodic monitoring by UTMB's Conflict of Interest Committee. The subjects' right to confidentiality will be protected at all times and no subject will be identified by name in any publication that results from this research.

13. Potential Benefits:

The only potential benefits for the participation in this protocol are related to the knowledge of the results of the screening tests that will be released to the volunteer. The knowledge collected from the present studies may be of benefit to society, as these studies will help develop the scientific basis for designing treatments for reducing loss in muscle mass and function in older subjects with T2DM.

Importance of the Knowledge to be Gained. These studies will allow us to identify the biological mechanisms by T2DM accelerate sarcopenia in older individuals. Since T2DM is quite common in older adults and increase the risk of physical dependence, the knowledge to be gained will be very important to develop interventions to maintain independence in older adults.

13. Statistical Analysis:

Primary outcome variables will be measures of amino acid transport. All other variables will be treated as secondary outcomes. We will first compute the basal-to-acute treatment change for each variable in each subject. Experiment to test Aim 1 is designed using a 2×2 factorial approach with no repeated measures (see Table 1). A standard 2×2 ANOVA model will be used to test the main effects, treatment by group interactions, and contrasts of interest, particularly the interaction effect of EAA dose (Aim 1) on challenges to the metabolism by T2DM.

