Experiment for Aim 2 is designed using a 2×2 factorial approach with repeated measures across time (see Table 2). We will then use a standard repeated measures 2×2 ANOVA model to test the main effects, treatment by group interactions, and contrasts of interest, particularly the interaction effect of amino acid dose (Aim 1)/exercise (Aim 2) on the effect of bed rest. For each variable we will also test if there are basal differences between groups using one way ANOVA. If basal differences are found, we will then use the basal values as covariates. Factors such as age, sex, and BMI will also be considered as covariates. The same analytic plan will be used for secondary outcome variables, and the results will be used for the overall interpretation of our study. To further elucidate potentially important mechanistic relationships between the primary and secondary outcomes, along with their relationship to demographic characteristics such as sex, we will also use multiple regression models and other techniques, such as principal components analysis. Differences will be considered significant at $p<0.05$. Post-hoc testing will be carried out using the Tukey-Kramer test. All calculations will be conducted in SAS (version 9.2 or later; SAS Institute Inc., Cary, NC). As necessary, responses will be transformed to assure that model assumptions of normality and constant group variance are met. Results will be presented as mean \pm SD.

Table 2. Groups for Aim 2. Healthy and T2DM older adults will be randomized into two physical therapy groups: standard of care (Control) and Exercise. In all groups we will measure the effect of 7 g of EAA before and after 5 days of bed-rest, as described in Aim 1.

*same group randomized to 7 g of EAA in Experiment 2.

GROUP	PHYSICAL THERAPY	
	Control	Exercise
Control	BR-C7*	BR-ExC7
T2DM	BR-D7*	BR-ExD7

protein turnover and amino acid transport in bed rest and T2DM, we will balance groups by sex. In *Table 3* we report the expected differences as original or log transformed units, the SD, the calculated n/group and the n/group including subjects to offset the expected attrition of 12%.

Table 3. Sample size (n) per group, based on the primary outcome, to detect the expected smallest differences between groups (Δ_{min}) given the measured standard deviation (SD) of the difference, alpha=0.05 and beta=0.8. n= subjects/group, n+ = n/group including expected attrition rate.

Outcome Variable	Δ_{min}	SD	n	n+

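### A significance test on basal values chooses, variable by variable, between two different T2DM-versus-control comparisons

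*Combined protocol and SAP*

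**What the plan says.** Section 13 (Statistical Analysis) defines the response: "We will first compute the basal-to-acute treatment change for each variable in each subject". For Aim 1, a 2×2 ANOVA on that change "will be used to test the main effects, treatment by group interactions, and contrasts of interest". The text then adds a pretest, "For each variable we will also test if there are basal differences between groups using one way ANOVA", and its consequence: "If basal differences are found, we will then use the basal values as covariates". The general significance level is 0.05 and no separate level is given for the pretest. Pairwise comparisons follow: "Post-hoc testing will be carried out using the Tukey-Kramer test". Secondary outcomes get the same plan.

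The primary outcome is amino acid transport, which is more than one variable. Section 4 (Metabolic Experiment) uses the tracers to measure "amino acid transport rates through LAT1 (Phe, Leu), SNAT2 (Gly), and PAT1 (Gly").

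On allocation, Table 1 states "Older adults with T2DM and healthy controls will be randomized to two groups (n=8/group"), and Group Randomization likewise randomises recruited subjects to 7 g or 21 g. Section 3 reads differently: "Since data previously gathered on healthy subjects will serve as controls for T2DM subjects".

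No section says whether the unadjusted or the basal-adjusted result is the intended T2DM-versus-control estimate, or that both will be reported.

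**The concern.** In a randomised comparison, the change score and the basal-adjusted model estimate the same effect, so a pretest between them affects mainly precision. T2DM versus control is not randomised. If the groups differ at baseline, the unadjusted analysis asks whether mean changes differ. The adjusted analysis asks whether changes differ between people with the same basal value. Both questions are legitimate, but they can have different answers.

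Under the rule, a test on 8 subjects per cell decides which question is answered, separately for each variable. The contrasts affected are the T2DM main effect and the four T2DM-control pairs among the six Tukey-Kramer comparisons (D7 or D21 against C7 or C21). At stake is whether the reported T2DM estimate has a definable target, and whether the primary transport variables in one report answer the same question.

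**Working it through.** **Inputs from the documents.** Four cells of 8 (Table 1); alpha 0.05; per-variable one-way ANOVA pretest. Table 3 gives a difference of 0.52, SD 0.29, n = 6 and n+ = 8 for transporter expression.

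**Assumed, because the documents do not give them.** Basal T2DM-control gap, 0 to 1.5 SD; within-cell basal-acute correlation rho, 0.3 to 0.9; ratio of acute to basal SD, 1 to 1.5; tests two-sided.

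**The plan's own figure.** 0.52/0.29 = 1.79 SD. A two-sided two-sample t-test with 6 per group has power 0.799, so the stated n = 6 reproduces. Inflating for 12% attrition gives 6/0.88 = 6.8, or 7; the plan states 8, which is used here.

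**The two estimates.** Let b be the within-cell slope of acute on basal, b = rho × (acute SD / basal SD).
- Unadjusted: acute difference − basal gap.
- Adjusted: acute difference − b × basal gap.
- Adjusted minus unadjusted: basal gap × (1 − b).

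With a gap of 1 SD and b = 0.5 they differ by 1 × (1 − 0.5) = 0.50 SD.

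**How often the pretest fires.** With equal cells the noncentrality is 32 × (gap/2)² = 8 × gap², on 3 and 28 degrees of freedom. Gaps of 0, 0.5, 1 and 1.5 SD give noncentralities of 0, 2, 8 and 18, and firing probabilities of 0.05, 0.17, 0.59 and 0.93.

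**Simulated T2DM main effect** (20,000 trials per row, 8 per cell, rho 0.5, equal SDs). Each triplet is change / planned rule / always adjusted.

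| True state | Gap (SD) | Mean estimate (SD) | Rejection (%) |
|---|---|---|---|
| Equal change | 0 | 0 / 0 / 0 | 4.9 / 4.6 / 4.9 |
| Equal change | 0.5 | 0 / 0.08 / 0.25 | 5.0 / 5.4 / 11.7 |
| Equal change | 1.0 | 0 / 0.36 / 0.50 | 4.9 / 17.6 / 28.7 |
| No effect at equal basal value | 0.5 | −0.25 / −0.17 / 0 | 10.8 / 7.5 / 5.1 |
| No effect at equal basal value | 1.0 | −0.50 / −0.15 / 0 | 28.3 / 8.6 / 5.0 |

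A repeat run of the third row gave 0.35 SD and 16.7%. Its parts reconcile: the estimate averages 0.50 when the pretest fires and 0.14 when it does not, and 0.59 × 0.50 + 0.41 × 0.14 = 0.35.

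**One pair, D7 versus C7, same setting and equal change.** Unadjusted for multiplicity, the rule rejects 12%, against 5% for change and 18% for always adjusted. With Tukey-Kramer the figures are 3.6%, 1.1% and 6.1%.

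**Sensitivity at a 1 SD gap, equal change.** Over rho 0.3 to 0.9 and SD ratios 1 to 1.5 (slopes 0.30 to 1.35), the rule's average runs from 0.49 to −0.24 SD, near 0 when the slope is near 1. Rejection runs from 5% to 25%. If the 80 subjects in section 3 were split evenly over six cells (an assumption, about 13 each), then at rho 0.5 the pretest fires 84%, the average is 0.46 SD and rejection is 37%.

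**Agreement between variables.** For three primary variables (assumed) at a 1 SD gap, the chance that they do not all take the same branch is 73% if they are independent and 33% if their basal values correlate 0.8. Phe and Leu share LAT1, so the lower figure is the more plausible.

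**Interaction.** Under no dose-by-T2DM interaction, the rule rejects in 4.3% to 5.3% of trials.

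**The case against.** The strongest reply is that the plan's stated interest lies elsewhere. Section 13 singles out the dose-by-T2DM interaction, and section 2 frames Aim 1 as sensitivity to increasing doses. That stands. A reader might infer that the pretest biases the dose or exercise contrasts or the interaction. It does not: with dose and therapy randomised within both groups, the two models agree on average and the type I error holds. Only some precision is at stake. But section 13 also plans main effects, contrasts and pairwise tests, and those include the T2DM-versus-control comparisons.

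Second, the size depends on an assumed basal gap. Section 4 says T2DM involves high glucose and insulin, inflammation and endothelial dysfunction, but gives no gap for amino acid transport. This also stands. The effect is small at 0.5 SD, absent with no gap, and its sign depends on the slope.

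Third, a reader might conclude that the reported result can have no valid error rate. That goes too far. If the report says which branch was taken, each branch rejects about 5% under its own null at 8 per cell and a 1 SD gap. Two problems remain: a bias of about 0.14 SD for the change estimate when the pretest does not fire, and a question that can vary between variables.

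Fourth, Aim 2 gives each subject a basal value before and another after bed rest, and the plan does not say which would be the covariate. A reader might infer a definite bias in the exercise contrast from adjusting for the second. The documents do not support a figure: they do not say the second is meant, and the rule adjusts only when the pretest fires.

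**Conclusion.** The concern holds for the non-randomised T2DM-versus-control contrasts only. If a moderate basal gap exists, the rule reports a data-selected mixture of two quantities. Taken without regard to the branch, it exceeds 5% rejection under either null: about 17% and 9% at an assumed 1 SD gap and correlation 0.5. With equal true changes and a 0.5 SD gap, the distortion is about 0.08 SD with rejection near 5%. With no gap or a slope near 1 there is no bias. These sizes are conditional on assumed values. The absence of one named T2DM estimand is plain from the text and does not depend on them.

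The statement that dose, exercise and interaction contrasts are unbiased requires controls to be randomised as Table 1 and Group Randomization say. Section 3 describes previously gathered healthy data as the controls. That is a separate inconsistency, and the passages must be reconciled.

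**What to change.** Delete the pretest and name one model in advance, the same for every variable. Take all contrasts in a Tukey-Kramer family from that model, so that cell means and error terms are common to all six pairs. One option is always to include the pre-intervention basal value as covariate, with the unadjusted-change T2DM-versus-control contrasts reported alongside as a sensitivity analysis. If unadjusted change is named as the T2DM estimand, reverse the roles.

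In Aim 2, if a basal covariate is used, use only the pre-bed-rest value, because the later one follows the randomised therapy. Enter it with a basal-by-time term. In a check on one simulated data set, a constant covariate left the exercise-by-time estimate unchanged (0.6064 with and without it). With the by-time term, the standard error ranges from 7% smaller to 1% larger over correlations 0.3 to 0.9, so little precision is gained there.

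State separately whether the healthy controls are newly randomised or previously gathered.

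The cost is SAP wording; basal values are already collected. Always adjusting uses one of the 28 error degrees of freedom in Aim 1 (32 subjects less 4 cell means). Reading Table 3's 0.52/0.29 as a between-group difference, with 8 per cell, no gap and equal SDs, power for D21 versus D7 is 94% to 99% always adjusted, against 93% to 94% under the rule. In the least favourable assumed setting (acute SD 1.5 times basal, rho 0.7), always adjusting loses 0.6 points, or 1.3 points if 0.52/0.29 were read as the interaction.
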